## 4.2.3 Exploratory Endpoint

Comparison planning with proton radiation will also be performed, to explore whether superior functional lung sparing can be achieved with proton radiation, compared with conventional photon radiation therapy. Two planning paradigms will be utilized: (1) fixed tumor dose objectives and comparison of normal tissue dose sparing, (2) fixed normal tissue objectives and comparison of tumor dose escalation.

# 5.0 SUBJECT SELECTION

## 5.1 Inclusion Criteria

- 5.1.1 Lung cancer patients receiving radiation treatment to the thorax to at least 45 Gy. Both non-small cell and small cell patients are eligible. Patient must have pathologic confirmation of diagnosis, or have an enlarging lung mass on at least two scans spaced 3 months apart, and FDG avidity on PET scan.
- 5.1.2 All stages of lung cancer are eligible, but patients must be planned for at least 45 Gy of radiation.
- 5.1.3 Patients are not required to have measurable disease. Post-operative patients (patients who have had surgical resection of lung cancer) are eligible.
- 5.1.4 Patients must have pulmonary function as defined below:
  - 5.1.4.1 Abnormal pulmonary function test within 3 months of study entry
  - 5.1.4.2 Prior radiation to the lungs
  - 5.1.4.3 Prior surgical resection of lung tissue (i.e. wedge resection, lobectomy, or pneumonectomy)
  - 5.1.4.4 Clinical diagnosis of COPD or emphysema
  - 5.1.4.5 Ongoing oxygen use
- 5.1.5 There are no limits on prior therapy. Patients are allowed to have prior chemotherapy, radiation therapy, and surgery. Patients are allowed to have concurrent chemotherapy with radiation treatment. Patients are allowed to have chemotherapy after radiation treatment. Patients are not allowed to have planned lung resection after radiation.
- 5.1.6 Patients >18 years old.
- 5.1.7 Ability to understand and the willingness to sign a written informed consent document.

- 5.1.8 Patients will typically be enrolled on this trial prior to beginning the radiation treatment course. However, if a patient has had a SPECT/CT 99mTc-MAA and 99mTc-DTPA scan as part of routine medical care within 6 weeks prior to initiation of radiation treatment, he/she is eligible for trial enrollment up to the last day of the radiation treatment course.

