## 3.0 STUDY OBJECTIVES

### 3.1 Primary Objective

To utilize SPECT/CT imaging with  $^{99m}\text{Tc}$ -MAA and  $^{99m}\text{Tc}$ -DTPA to identify functional lung on serial imaging in patients receiving radiation treatment for lung cancer, as well as to characterize reproducibility of perfusion and ventilation in non-irradiated lung tissue.

Hypothesis: For lung tissue outside the radiation field, perfusion and ventilation as defined by SPECT/CT imaging with  $^{99m}\text{Tc}$ -MAA and  $^{99m}\text{Tc}$ -DTPA will exhibit smaller changes over time than tissue inside the radiation field. Compared to the pre-radiation scan, lung tissue receiving radiation dose below the 20th percentile of total lung will have perfusion and ventilation that remain constant or increase at the mid-radiation treatment scan and 3-months post-treatment scans. By contrast, lung tissue receiving radiation dose above the 80th percentile of total lung will have perfusion and ventilation that decrease at the mid-radiation treatment scans and 3-months post-treatment scans.

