### 4.2 Endpoints

#### 4.2.1 Primary Endpoint

In this study, patients with lung cancer will undergo SPECT/CT imaging with  $^{99m}\text{Tc}$ -MAA and  $^{99m}\text{Tc}$ -DTPA at the time of radiation treatment planning. All image datasets will be imported into MIM 6.0, and fused with the radiation treatment planning CT and radiation plan. Lung tissue will be divided into tissue outside the radiation field (dose < 20th percentile of total lung dose) and tissue inside the radiation field (dose > 80th percentile of total lung dose). This process will be repeated for the mid-treatment scan and 3 months post-treatment scan. Lung tissue outside the radiation field will be compared on serial scans and their perfusion and ventilation quantified. There should be insignificant changes in perfusion and ventilation in >80% of lung tissue outside the radiation field. Lung tissue inside the radiation field will also be compared, and should yield significant differences in ventilation and perfusion between pre, mid, and post-treatment scans.

We will analyze the perfusion and ventilation data through multiple methods. Image sets from all 3 time points (before radiation, mid-radiation, 3-months post-radiation) will be fused using rigid registration. Regions of interest within the lung will be defined using automated and semi-automated methods, including simple thresholds and gradient-search algorithms. For each tracer, uptake value will be calculated for each voxel. For lung tissue outside the radiation field, summary statistics such as total regional uptake and mean regional uptake by lobe will be compared across the time points using parametric and non-parametric statistical testing. Voxel-based correlation, including Pearson linear and Spearman rank, will be performed to measure the stability of uptake between time points. Lastly, metrics of ventilation and perfusion volume overlap between time points will be estimated using the Dice coefficient.

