## **5.2 Exclusion Criteria**

- 5.2.1 Patients must not be planned for lung resection after radiation therapy.
- 5.2.2 Patients receiving < 45 Gy radiation.
- 5.2.3 Patients who received radiation to the chest within the past 6 months.
- 5.2.4 Patients unable to tolerate a SPECT/CT 99mTc-MAA and 99mTc-DTPA scan.
- 5.2.5 Patients who are not planning to adhere to the required follow up schedule as outlined in this protocol.
- 5.2.6 Pregnant women
- 5.2.7 Women of childbearing potential and men who are sexually active and not willing/able to use medically acceptable forms of contraception.
- 5.2.8 Patients unable to provide informed consent.

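### Patients can qualify through prior lung radiation, yet the outside-field region is defined from one radiation plan, so previously irradiated lung can be counted as non-irradiated

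*Combined protocol and SAP*

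**What the plan says.** Section 5.1.4 lists five conditions relating to pulmonary function, and 5.1.4.2 is "Prior radiation to the lungs". It does not say whether one or all are needed; any one is the plausible reading. Section 5.1.5 adds: "There are no limits on prior therapy. Patients are allowed to have prior chemotherapy, radiation therapy, and surgery". The only restriction on earlier chest radiation is exclusion 5.2.3: "Patients who received radiation to the chest within the past 6 months".

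One aim of the primary objective (3.1) is "to characterize reproducibility of perfusion and ventilation in non-irradiated lung tissue". Section 4.2.1 puts this into practice by having the images "fused with the radiation treatment planning CT and radiation plan", and then: "Lung tissue will be divided into tissue outside the radiation field" (below the 20th percentile of lung dose) and tissue inside it (above the 80th). The expected result is: "There should be insignificant changes in perfusion and ventilation in >80% of lung tissue outside the radiation field".

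Section 4.2.2 addresses secondary aims (a) and (b) in lung inside the field. It plots change from the baseline scan against radiation dose, then draws separate curves for the upper and lower quartiles of ventilation and perfusion. No section mentions earlier plans, summed dose, masking of old fields, adjustment for prior radiation, or an analysis without these patients.

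**The concern.** The rule that builds the outside-field region does not guarantee the tissue that objective 3.1 is about. A voxel treated a year earlier and receiving little dose now meets the 4.2.1 definition, although it is not non-irradiated lung. Section 2.2 states that radiation affects both ventilation and perfusion, so on the protocol's own premise earlier dose is relevant.

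Two results are exposed, through different tissue. The primary stability result is exposed through old-field lung in the current low-dose region. The dose-response work under 3.2(a) and 3.2(b) is exposed through old-field lung that overlaps the current high-dose region: its plotted dose is too low, and its low baseline uptake may be partly a radiation effect. Objective 3.2(b) hopes to find lung that can be treated with little functional cost, so what makes up the low-function group matters.

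**Working it through.** The plan gives no figure to reproduce here. The first step compares definitions. The rest is illustration, and apart from the 20 evaluable subjects (section 1.0), the percentile cut-offs and the >80% criterion, every input is assumed.

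**1. Where old-field lung goes under 4.2.1 and 4.2.2**

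| Current dose to the old-field voxel | Treatment in the plan | Consequence |
|---|---|---|
| Below 20th percentile | Outside field | Counted as non-irradiated (3.1) |
| 20th to 80th percentile | Neither region | Not in the outside/inside comparison |
| Above 80th percentile | Inside field | Prior dose missing from the axis; baseline uptake may be lowered |

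No voxel can be in the first and third rows at once, so the two problems concern different tissue.

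**2. How many patients.** If a proportion q enters with prior lung radiation, the expected number is 20q and P(at least one) = 1 − (1 − q)^20.

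| q (assumed) | Expected of 20 | P(at least one) |
|---|---|---|
| 5% | 1 | 0.64 |
| 10% | 2 | 0.88 |
| 20% | 4 | 0.99 |

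**3. The >80% criterion in one patient.** Let b be the share of never-irradiated outside-field lung that changes, u the share of old-field lung there that changes, and s the old-field share of the region. Then

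stable share = 1 − (1 − s)b − s·u,

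which reaches 0.80 at s = (0.20 − b)/(u − b).

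| b | u | s at which the stable share is 80% |
|---|---|---|
| 0.10 | 0.30 | 0.10/0.20 = 0.50 |
| 0.10 | 0.50 | 0.10/0.40 = 0.25 |
| 0.15 | 0.30 | 0.05/0.15 = 0.33 |
| 0.15 | 0.50 | 0.05/0.35 = 0.14 |

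If the percentile is taken over lung volume, the outside-field region is 20% of the lung, so these shares are 0.14 × 20% = 2.8% to 0.50 × 20% = 10% of total lung. If u ≤ b, old-field tissue does not lower the stable share.

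**4. The same criterion pooled over patients.** Suppose 4 of 20 patients are affected, half of each one's outside-field region is old-field lung, and volumes are equal. Then s = (4/20) × 0.5 = 0.10. The shift is s(u − b), from 0.10 × 0.15 = 0.015 to 0.10 × 0.40 = 0.04, and the four scenarios give stable shares of 0.88, 0.86, 0.835 and 0.815. All stay above 0.80. Pooled, the effect is a shift of 1.5 to 4 percentage points; in single patients it can decide the result.

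**5. The 3.2(b) contrast.** Let c be the old-field share of the tissue actually compared, that is, the overlap with the current field. In a simulation with log-normal uptake (log-SD 0.4), c of 10% to 30% and uptake lowered by 10% to 50%, old-field tissue makes up 13% to 76% of the lower quartile and 0.4% to 23% of the upper. With shares pL and pU in the two quartiles, no difference in slope among never-irradiated voxels, and an old-field slope k times theirs, the apparent slope ratio is [1 − (1 − k)pL]/[1 − (1 − k)pU]. At c = 30% and uptake lowered by 50%, pL = 0.764 and pU = 0.021:

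- k = 0.5: 0.618/0.9895 = 0.62
- k = 1.5: 1.382/1.0105 = 1.37
- k = 1: ratio 1, no distortion from this source

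With no overlap (c = 0) the problem does not arise.

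**The case against.** The strongest reply is that the primary endpoint is change from the current baseline scan and that recent chest radiation is excluded. Established damage is then already in the baseline, and only tissue still changing can disturb the stability result. This stands: with u ≤ b there is no downward bias. But nothing in the plan shows that old-field lung is stable after 6 months, and the quartile split uses uptake level, which a change score does not correct.

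Second, reliance on the current plan alone is inferred from the singular wording and from silence; dose accumulation is not ruled out. That is fair, but an analyst following 4.2.1 as written would not perform it.

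Third, 3.2(b) compares well and poorly functioning lung whatever the cause, so old-field lung may belong in the low group. This also stands, and is a reason to label such voxels there rather than delete them. The documents offer nothing on whether re-irradiated lung responds differently, so k above is purely an assumption.

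A reader might also infer that an old field covering 20% of the lung could supply 20/25 = 80% of the lower quartile. The documents do not support that figure: it uses whole lung, while 4.2.2 sets aims (a) and (b) inside the current field, so only the overlap counts.

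**Conclusion.** The concern holds as a mismatch between a stated region rule and the stated target tissue. As written, section 4.2.1 can place previously irradiated lung in the region that represents non-irradiated lung, and no other section corrects it. Where fields overlap, the dose plotted under 4.2.2 is too low and low baseline uptake may partly reflect earlier radiation.

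The size cannot be stated. It depends on how many patients enter this way, where their old fields lie, whether that tissue is still changing (primary result), and how far it overlaps the current field (3.2). Under the assumptions above, it could decide the >80% criterion in individual patients and would move a pooled figure by a few percentage points.

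A reader might go further and conclude that the primary result is biased, or that the trial preferentially recruits re-irradiated patients. Neither follows: the bias is conditional, and prior radiation is on the plausible reading one of five routes in, possibly used by no one. The matter should be settled before analysis because, with 20 evaluable subjects, a later decision to drop a few patients would be hard to defend.

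**What to change.** In sections 4.2.1 and 4.2.2:

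- Record for every patient whether there was prior lung radiation and, where plans can be retrieved, the location of the earlier fields.
- Exclude voxels within a known prior field from the outside-field region.
- Label those voxels separately in the upper versus lower quartile comparison.
- Pre-specify a sensitivity analysis of the primary result and of the 3.2(b) contrast that leaves out patients with prior lung radiation. Where a prior field cannot be located, rely on this analysis.

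Summing prior and current dose is optional. It would require registering old planning scans to present anatomy, possibly after resection, when 4.2.1 plans rigid registration only, and combining different fractionation schedules.

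The cost is retrieval of existing plans, approximate registration of old fields, and some loss of precision in the affected analyses. Eligibility, imaging and treatment are unchanged.

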## **5.2 Exclusion Criteria**

- 5.2.1 Patients must not be planned for lung resection after radiation therapy.
- 5.2.2 Patients receiving < 45 Gy radiation.
- 5.2.3 Patients who received radiation to the chest within the past 6 months.
- 5.2.4 Patients unable to tolerate a SPECT/CT 99mTc-MAA and 99mTc-DTPA scan.
- 5.2.5 Patients who are not planning to adhere to the required follow up schedule as outlined in this protocol.
- 5.2.6 Pregnant women
- 5.2.7 Women of childbearing potential and men who are sexually active and not willing/able to use medically acceptable forms of contraception.
- 5.2.8 Patients unable to provide informed consent.

## **5.3 Recruitment**

Subjects will be recruited from investigator clinical practices and include men and women with lung cancer who will be receiving radiotherapy to at least 45 Gy. Subjects will undergo an informed consent process in accordance with GCP (see section 11 Ethical Considerations). Informed consent will be obtained prior to the performance of any screening procedures.

## **6.0 SUBJECT REGISTRATION**

Subjects will be registered by the FHCRC/UW Study Coordinator and entered into the Protocol Accrual Tracking System (PATS). Information regarding the PATS system is available at [http://www.cancerconsortiumorg/rto/protocol\\_office/pats/](http://www.cancerconsortiumorg/rto/protocol_office/pats/). A complete, signed, study consent and HIPAA consent are required for registration.

## **7.0 TREATMENT PLAN**

All patients will receive radiation treatment per standard of care. As part of this study, all patients will undergo 3 SPECT/CT scans: 1) first scan will be at the time of radiation treatment planning, in the treatment position. This scan will be standard of care clinically for patients with compromised lung function (such as COPD); 2) second scan will be mid-radiation treatment (up to 1 week post-completion of radiation is acceptable), to assess the acute response of functional lung to radiation; 3) third scan will be 3 months post-radiation (up to 6 months is acceptable), to assess the longer term response of functional lung tissue. Follow up of all patients will occur via standard clinical follow-up by treating physician. This clinical follow-up may include clinical exam, pulmonary function test (PFT), and FDG PET/CT scan. Research staff will review clinical record at 3 months post-treatment. See Table 1 below for summary.

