## **7.1 Imaging Protocol**

SPECT/CT with 99mTc-MAA and 99mTc-DTPA will be performed per standard protocol, which is currently in routine clinical use. The imaging session is comprised of an inhalation of the 99mTc-DTPA tracer and SPECT static acquisition, followed by intravenous injection of the 99mTc-MAA tracer and second SPECT static acquisition. This rapid serial process ensures the efficient imaging of ventilation and perfusion in the same imaging session. An initial scan at the time of radiation planning will identify functional lung that is ventilated and perfused. This scan will be in the radiation treatment position which can be fused precisely with the radiation treatment planning scan, and will be used to identify functional lung tissue both inside and outside the radiation fields. Two follow up scans will track lung response to radiation (one scan at mid-treatment for acute radiation response, and one scan at 3-months post-treatment for longer term assessment). Detailed ventilation and perfusion dose response curves will be generated from this data. Comparison planning with proton radiation will be performed to evaluate the feasibility of improved functional lung sparing with proton beam radiation.

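### Treatment position is required for the first scan only and all scans are fused rigidly, so residual posture, breathing or shape differences can be read as functional change in the voxel-level analyses

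*Combined protocol and SAP*

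**What the plan says.** **First scan.** Section 7.0 states that the "first scan will be at the time of radiation treatment planning, in the treatment position". Section 7.1 gives the purpose: "This scan will be in the radiation treatment position which can be fused precisely with the radiation treatment planning scan".

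**Later scans.** Section 7.0 gives timing only: "second scan will be mid-radiation treatment (up to 1 week post-completion of radiation is acceptable" and "third scan will be 3 months post-radiation (up to 6 months is acceptable". Section 7.1 adds "Two follow up scans will track lung response to radiation" but no position. Its one general acquisition rule is that SPECT/CT follows the protocol in routine clinical use.

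**Late enrolment.** Section 5.1.8 covers a patient already imaged "as part of routine medical care within 6 weeks prior to initiation of radiation treatment, he/she is eligible for trial enrollment". Such a patient can join at any point until radiotherapy ends. No position condition is attached.

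**Analysis.** Section 4.2.1 says that the image sets "will be fused using rigid registration". It then measures stability by voxel-wise Pearson and Spearman correlation, Dice overlap, and total and mean uptake by lobe. It expects more than 80% of out-of-field lung to show no meaningful change. Section 4.2.2 relates change from baseline to dose at global, regional and voxel scales.

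The plan describes no registration-accuracy check, no rule on breathing state, no test-retest error and no sensitivity analysis on position.

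**The concern.** Voxel correlation, Dice and voxel-scale dose response all assume that one coordinate holds the same tissue at each time point. A rigid transform translates and rotates the whole image. It cannot undo a different arm position, a different depth of breathing, tumour shrinkage or loss of lung volume, and the last scan may fall as late as 6 months after radiation. Nothing in the plan separates what is left over from a real change in function.

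Three results are exposed:

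- **Stability of out-of-field lung (primary).** Misalignment lowers correlation and Dice in lung that has not changed.
- **Voxel dose response (objective 3.2(a)).** Change is attributed to the wrong dose where dose varies steeply, which tends to flatten the curve. Imaging in the treatment position is part of the advantage that this hypothesis claims.
- **Well-functioning against poorly functioning lung (objective 3.2(b)).** Groups are defined by quartiles of uptake. If these are baseline quartiles, misalignment pulls both extremes towards the middle, so the two groups appear to change differently when neither has.

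**Working it through.** **1. Is there a figure to reproduce?** No. The documents give no registration error, image resolution or cut-off for a voxel change. The check is a comparison of the text, followed by illustrations on assumed values.

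**2. The sections side by side.**

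| Item | Position stated? | Where |
|---|---|---|
| Scan 1 | Yes, treatment position | 7.0, 7.1 |
| Routine scan used as baseline | Not stated | 5.1.8 |
| Scan 2 | Not stated | 7.0, 7.1 |
| Scan 3 | Not stated | 7.0, 7.1 |
| Fusion of all three | Rigid | 4.2.1 |

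**3. Voxel correlation, function unchanged.** For a Gaussian-smoothed field compared with itself at local offset d, r = exp(−d²/(4s²)), with s = FWHM/2.355. The FWHM and d are assumptions. Worked case: FWHM 15 mm gives s = 6.37 mm and 4s² = 162.3, so at d = 10 mm, r = exp(−100/162.3) = 0.54.

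| Offset | FWHM 15 mm | 20 mm | 30 mm | 40 mm |
|---|---|---|---|---|
| 5 mm | 0.86 | 0.92 | 0.96 | 0.98 |
| 10 mm | 0.54 | 0.71 | 0.86 | 0.92 |

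A simulated field gave the same values to two decimals at FWHM 20 and 40 mm.

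**4. Dice, function unchanged.**

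- Slab of thickness t: 1 − d/t. With d = 10 and t = 60 mm, 1 − 10/60 = 0.83.
- Sphere of radius r: 1 − 3d/(4r) + d³/(16r³). At d = 10 mm, r = 30 mm gives 1 − 0.25 + 0.002 = 0.75, and r = 50 mm gives 1 − 0.15 + 0.0005 = 0.85.
- Concentric volume loss to a fraction v, with no shift: 2v/(1 + v). A 10% loss gives 1.8/1.9 = 0.95, and a 30% loss gives 1.4/1.7 = 0.82.

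The last line needs no offset. It shows that shape change alone lowers Dice even if position is matched.

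**5. Apparent change in a simulated, unchanged field.** The field had coefficient of variation 30% and 4 mm voxels, and was compared with itself after a residual shift. The cut-off of 20% for a change is an assumption. Each cell gives FWHM 20 mm / 40 mm.

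| Offset | Voxels changed by more than 20% | Lowest baseline quartile | Highest baseline quartile |
|---|---|---|---|
| 5 mm | 13.1% / 1.2% | +5.7% / +1.4% | −2.5% / −0.6% |
| 10 mm | 38.4% / 12.1% | +18.7% / +4.9% | −8.2% / −2.3% |
| 15 mm | 51.9% / 26.5% | +34.1% / +10.2% | −15.0% / −4.7% |
| 20 mm | 58.6% / 38.1% | +47.5% / +16.8% | −20.8% / −7.8% |

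If the 80% expectation is applied to voxels with this cut-off, unchanged lung meets it in both fields at 5 mm. At 10 mm it fails in the finer field (100 − 38.4 = 61.6% unchanged) and passes in the smoother one (87.9%). At 15 mm it fails in both. The whole-field mean did not change at any offset, which is why global summaries, and to a large extent lobe summaries, are protected.

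**The case against.** **Section 5.1.8 does not waive the position.** A reader might infer that the protocol exempts late-enrolled patients. The documents do not say so. Sections 4.1 and 7.0 describe scan 1 itself as routine or standard care, so 5.1.8 may simply allow late consent for a patient who already had that scan. A planning-position scan done within the 6 weeks satisfies both sections. This stands. What remains is that 5.1.8 is silent, that the scan may predate enrolment, and that nothing says what happens to a baseline acquired otherwise.

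**The intent to scan in position is visible.** A reader might infer that scans 2 and 3 are planned in a different posture. Sections 2.2 and 3.2(a) refer in general terms to SPECT/CT in the treatment position, and the reference in 7.1 to routine practice covers scan 1 too. This also stands. An intention in the rationale or in a hypothesis is still not an acquisition rule.

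**The illustrations use uniform shifts.** Rigid fusion is designed to remove a uniform shift, so the figures apply only to local misalignment that remains after it. Real residual deformation varies across the lung, and coarse regional patterns would be more robust than fine texture. The figures are therefore no estimate of the error in this trial.

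**Other analyses are protected, and the bias can be conservative.** Lobe and global summaries are much less affected. The primary strata leave out the middle 60% of the dose distribution, which limits mixing across gradients. For the stability claim, misalignment works against the hypothesis. All of this stands, but the distortion of the quartile contrast is not conservative: it can mimic a difference.

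**Deformable registration has its own error** in lung that has changed shape. This is a reason to use it as a sensitivity analysis and keep rigid fusion as the main method.

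**Conclusion.** The concern holds as a gap in acquisition and analysis rules. Position is fixed for one scan of three, the status of a routine baseline scan is left open, and rigid fusion leaves posture, breathing and shape differences uncorrected. In the voxel correlation, Dice and voxel-scale dose-response analyses, these differences can be read as functional change.

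The size is unknown. On the assumed offsets and smoothness the effect ranges from negligible (5 mm, smooth field) to large enough to miss the 80% expectation with no functional change (15 mm and above in both fields). That range rests on assumed residual local misalignment, an assumed 20% cut-off and a voxel-level reading of the criterion.

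A reader might go further and conclude that the primary result is invalid. The documents do not support that, because 4.2.1 and 4.2.2 also include lobe-level, regional and global summaries. The point should be settled before patients are scanned, because position cannot be changed afterwards and only 20 evaluable subjects are planned.

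**What to change.** 1. State in 7.0 and 7.1 that scans 2 and 3 are acquired in the same treatment position and immobilisation as scan 1.
2. Reconcile 5.1.8 with 7.0, and record the position of any routine scan used as baseline. Where it was not the treatment position, repeat the voxel-level and Dice analyses without that patient, and keep the patient in the lobe-level and global analyses.
3. Keep rigid fusion as the main method. Repeat the voxel and Dice results with CT-based deformable registration as a sensitivity analysis, using the CT that each SPECT/CT already provides. This is needed even if position is matched, because matching does not remove breathing or volume differences.

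**Cost.** Set-up takes slightly longer, and there is one repeat analysis, which brings its own registration error. The sensitivity analysis has a smaller voxel-level set; the documents do not show how many patients would be affected. No additional scan is needed.
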